Baseline data will be recorded on a self-administered questionnaire containing queries relating to the participant's state of health and potential risk factors. Demographic data, medical and gynecological history, detailed history of previous treatments for endometriosis, anemia and psychiatric illnesses, medication history and family history of depression and anemia/hematological problems as well as the addresses, e-mail addresses and phone numbers of the patient, relatives or friends, and the primary care physician are to be provided. In compliance with data protection regulations names, addresses and phone numbers are to be documented on a separate sheet and stored separately in a locked cabinet.

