## 3.3 Study variables

Table 1: Schedule of assessments and variables obtained during study phases.

	Ph	ase I	Phase II
	Baseline		FU 1
	Dd	seille	up to FU 8
	Physician	Patient	Patient
Informed consent		Before any procedure	
Patient characteristics			
- Age of women		х	
- Height			
- Weight		v	v
- BMI		Х	X
Socio-economic characteristics			
- Education		х	
- Smoking			
Endometriosis treatment	X		
- Diagnosis classification			

 
Prescribed medication
 
			

 
Number of surgical procedures (related to
 
	x		x
endometriosis)			

 
Reasons for switching / stopping treatment
 
			Х
Endometriosis characteristics			

 
Endometriosis pattern (symptoms, first
 
		х	
diagnosis, treatment history, pain)			

 
Surgical procedures related to endometriosis
 
		Х	Х
Gynecological History			

 
Age at first menarche
 
		х	

 
Pregnancies/deliveries
 
			
Medical history			
- Diseases / conditions		v	

 
Surgical procedures (other than
 
		X	
endometriosis-related)			
Family history		v	
(Endometriosis, Depression, VTE)		Х	
Medication		Х	Х
Anemia		Х	Х
Depression		Х	Х
Mood		Х	Х
Serious Adverse events			Х

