#### 5.4.2 Regression models

Regression analysis will be performed if a sufficient number of confirmed events are available for estimation, i.e. n≥5 confirmed events in each of the comparison groups.

Potential confounders such as

- age, personal and family history of depression, history of anemia, history of bleeding disorders and severity of pain will be included as time-invariant cofactors.
- EMT user type at follow up, use of Antidepressants/SSRI and current or worsening depression (primary outcome) will be included as time-dependent cofactors.

For each primary outcome, a summary table with predefined potential prognostic factors and the corresponding relative risk estimators is provided.

The final decision on the confounding variables will be made by the Safety Monitoring and Advisory Council:

Primary outcome variable	Predefined Prognostic Factors 	
Anemia	Age, history of anemia, history of bleeding disorders	
Depression	Age, family and personal history of depression, use of Antidepressants/SSRI	
Treatment Failure	Age, family and personal history of depression, severity of pain	

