11.	What symptoms do you have associated wit	th your end	ometriosis	? (plea	ase tick all that apply)	
	$\Box$ Pelvic pain unrelated to period pain $_{\rm 22}$		□ Pain v	vhen pa	assing urine 27	
	☐ Experienced pain during or after sexual inter	course 23	☐ Pain d	luring b	owel movement 28	
	☐ Difficulty conceiving/infertility 24		☐ Const	ipation	or diarrhoea 29	
	☐ Painful periods 25		☐ Tiredn	iess / V	Veakness 30	
	$\square$ Heavy or irregular bleeding $_{26}$		☐ Other;	which	31 32	
12.	Have you had disabling pain associated with events on least two days in the last 4 weeks		metriosis	preve	nting you from working or attending social	
	□ No □ Yes					
13.	Please rate the pain associated with your er last 4 weeks, with 0 being no pain and 10 be				box that best describes your pain over the	
	no pain 0 1 2 3 4 5	6	7	9	unbearable pain	
14.	Have you had an operation to diagnose and		ur endome	triosis	? 35	
	□ No → go on to question 15	☐ Yes				
	If yes, please list the operation (if known) and t removal of ovarian cyst, hysterectomy, colonos For additional space, use comment section on page 4.					
	Operation 36				Date	
					M M J 37 Y Y Y Y 38	
					M M Y Y Y Y	
					M M Y Y Y Y Y	
					M M Y Y Y Y Y	
15.	Before today's prescription, have you been	prescribed	any other	medic		
	□ No → go on to question 16	☐ Yes				
	If yes , please list all the prescribed medication contraceptive, IUD, progestine, GnRH). Also give section on page 4.					
Na	me (type) of medication 40		from		to	
		M M 41	Y Y Y	Y J 42	M M 43 Y Y Y Y Y 44 □ ongoing 45	
		M M month	Y Y Y year	Y	M,M, Y,Y,Y,Y ☐ ongoing	
		M M L	Y Y Y	Υ	M,M (Y, Y, Y, Y) ☐ ongoing	
		M M L	Y Y Y Y	Υ	M M Y Y Y Y Y ☐ ongoing	
Med	lication					
16.	Are you taking any other medication on a re	gular basis	? (EXCLU	DING t	oday's prescription) 48	
	□ No □ Yes, which one(s)? (please use Trade Name if known)					
					47	
17.	Beyond today's prescribed medication, wha	t are you cu	irrently do	ing to	alleviate your endometriosis symptoms?	
	$\square$ Non-prescription pain killers $_{^{48}}$		Massage/	manual	therapy 52	
	☐ Natural/herbal products ₄9		Home rem	nedies (	(eg. hot water bottle) 53	
	☐ Acupuncture 50		Nothing el	se 54		
	☐ Dietary modification ₅1		Other; ple	ase spe	ecify 55 56	

2

Supporting document SOP BMT 01.09 – Doc 5002.02 – Effective date 21.03.2017

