## III List of potential prognostic factors for primary outcomes

Primary Outcome	Predefined Potential Prognostic Factors
Anemia	EMT user type at follow-up, age, history of anemia, history of bleeding disorders
Depression	EMT user type at follow-up, age, family and personal history of depression, use of Antidepressants/SSRI, severity of pain
Treatment Failure	EMT user type at follow-up, age, family and personal history of depression, current/worsening depression, severity of pain

Supporting document SOP BMT 01.09 – Doc 5002.02 – Effective date 21.03.2017

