### Section D Comparisons and Inferential Statistics of Primary Outcomes

#### Section D-1 New anemia and reoccurrence of anemia

Table D-1.1.1 Incidence rate ratio of new anemia and reoccurrence of anemia between EMT user cohorts, AT population

Comparison	Cohort	No. of	WY	Incidence	Incidence Rate Ratio
Group		events		rate*	(95% CI)
	DNG	xx	xxxxx	x.xxxx	x.xxxx
1	OAED	xx	xxxxx	x.xxxx	(x.xxxx - x.xxxx)
2	DNG NAED	xx xx	xxxxx	x.xxxx x.xxxx	x.xxxx (x.xxxx - x.xxxx)
2	DNG	xx	xxxxx	x.xxxx	x.xxxx
3	Ex-use	XX	xxxxx	x.xxxx	(x.xxxx - x.xxxx)

Note: \*Incidence rate per 10^4 women years

Supporting document SOP BMT 01.09 – Doc 5002.02 – Effective date 21.03.2017

Table D-1.1.2 Risk of new anemia and reoccurrence of anemia obtained from Cox model (HR), AT population

Cohort	No. of	No. of WYs		Hazard Ratio (95% CI)		
	events			Crude HR	Adjusted HR	
DNG	xx	xxxxx	x.xxxx	x.xxxx	x.xxxx	
OAED	XX	xxxxx	x.xxxx	(x.xxxx - x.xxxx)	(x.xxxx - x.xxxx)	
DNG	xx	xxxxx	x xxxx	x xxxx	X.XXXX	
NAED	xx	xxxxx	x.xxxx	(x.xxxx - x.xxxx)	(x.xxxx - x.xxxx)	
DNG	VV		V VVVV	V VVVV	V	
Ex-use	xx xx	XXXXX	x.xxxx x.xxxx	x.xxxx (x.xxxx - x.xxxx)	x.xxxx (x.xxxx - x.xxxx)	
	DNG OAED  DNG NAED	DNG XX DNG XX DNG XX DNG XX NAED XX	DNG XX XXXXX  DNG XX XXXXX  DNG XX XXXXX  DNG XX XXXXX  DNG XX XXXXX	DNG XX XXXXX X.XXXX OAED XX XXXXX X.XXXX  DNG XX XXXXX X.XXXX  NAED XX XXXXX X.XXXX  DNG XX XXXXX X.XXXX	DNG     XX     XXXXXX     XXXXXX     XXXXXX       OAED     XX     XXXXXX     XXXXXX     XXXXXX       DNG     XX     XXXXXX     XXXXXX     XXXXXX       NAED     XX     XXXXXX     XXXXXX     XXXXXX       DNG     XX     XXXXXX     XXXXXX     XXXXXX	

Note: \*Adjusted for age, history of bleeding and history of anemia.

Section D-2	New depression or deterioration of existing depression
	Incidence rate ratio of new depression or deterioration of existing depression between EMT user cohorts, AT population Risk of new depression or deterioration of existing depression obtained from the Cox model (HR), AT population
Section D-3	Treatment failure
Section D-3.1	Incidence rate ratio of treatment failure between EMT user cohorts, AT population
Section D-3.2	Risk of treatment failure obtained from the Cox model (HR), AT population

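### The bleeding covariate in the anemia model has no dedicated baseline item, derivation or consistent label, and the bleeding symptom that is collected is named in no covariate list

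*SAP*

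**What the plan says.** SAP 5.4.2 lists the predefined factors for anemia as "Age, history of anemia, history of bleeding disorders". It states that "history of anemia, history of bleeding disorders and severity of pain will be included as time-invariant cofactors", so the model needs a baseline value of the bleeding term for every woman. It adds that "The final decision on the confounding variables will be made by the Safety Monitoring and Advisory Council".

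Appendix III gives the list as "EMT user type at follow-up, age, history of anemia, history of bleeding disorders". The footnote to mock Table D-1.1.2, which will report the hazard ratio, reads "Adjusted for age, history of bleeding and history of anemia".

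Protocol section 11 names a different variable, a bleeding-disorder history in the family, together with the woman's own past anemia. Protocol section 6 planned to collect "family history of depression and anemia/hematological problems" at baseline. In the assessment schedule of SAP 3.3 the family history covers only "Endometriosis, Depression, VTE".

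The baseline questionnaire (SAP Appendix I) offers "Heavy or irregular bleeding" as one tick-box in question 11, among the symptoms associated with endometriosis.

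**The concern.** The anemia outcome is medical intervention for anemia induced by cyclical bleeding disturbances (SAP section 2). In a non-randomized comparison, bleeding at baseline plausibly predicts that outcome and could affect which drug is prescribed. The protocol introduction supports its relevance: it reports inter-menstrual spotting or bleeding in 72% of dienogest users in a 52-week open-label study, and a raised risk of menorrhagia in endometriosis.

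The model contains a bleeding term, so this appears to be covered. But a programmer following the SAP cannot tell which data field to use. If the term is filled from unprompted free text, it will adjust for little of the bleeding burden at baseline. What is at stake is the upper confidence limit of the adjusted anemia hazard ratio, which SAP 5.2 compares with 2.

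**Working it through.** **Tracing each covariate.** The plan gives no figure to reproduce. The check sets the covariates in SAP 5.4.2 against the places where they could be collected or derived.

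| Covariate | Dedicated baseline item | Derivation rule |
|---|---|---|
| Age | Question 5, date of birth | Categories in Appendix IV |
| History of anemia | Question 18, anemia line with treatment details | Not needed |
| History of bleeding disorders | None found | None |

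For the third row, these places were checked:

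- Questionnaire, gynecological history: age at first menstrual bleeding, pregnancies and births.
- Questionnaire, question 18: deep venous thrombosis, pulmonary embolism, infarction, stroke, anemia, depression, cancer, an open line for other serious diseases, and operations. The examples on the open line do not mention bleeding disorders.
- Family history: endometriosis, depression and thrombosis or embolism. The text of question 20 is broken in the copy available, but SAP 3.3 and mock Table B-5.1.1 identify it as depression.
- Mock Table B-5.2.1 (disease history): no bleeding-disorder row.
- Appendix IV, to which SAP 6.2.1 sends derived variables: no bleeding variable.

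**Comparing the labels.** Protocol section 11 has a family history of bleeding disorders. SAP 5.4.2 and Appendix III have a history of bleeding disorders, without saying whose. Table D-1.1.2 has a history of bleeding. These could be three different variables. The protocol's version cannot be built from the questionnaire, because no family item on bleeding or hematological problems appears there. SAP section 8 still lists family history of anemia under Section B-5.

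**Locating the collected item.** The tick-box in question 11 is tabulated in mock Table B-4.6.1 but is named in none of the covariate lists.

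**What an unadjusted imbalance could do.** The documents give neither bleeding prevalence by cohort nor anemia rates by bleeding status, so all inputs here are assumptions. Let *p*D and *p*O be the prevalence of heavy or irregular bleeding in the dienogest and comparator cohorts, and *k* the ratio of anemia rates with and without it. The crude rate ratio is multiplied by

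(*p*D × *k* + 1 − *p*D) / (*p*O × *k* + 1 − *p*O)

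| *p*D | *p*O | *k* | Factor |
|---|---|---|---|
| 0.30 | 0.50 | 4 | 1.9 / 2.5 = 0.76 |
| 0.40 | 0.50 | 4 | 2.2 / 2.5 = 0.88 |
| 0.30 | 0.50 | 2 | 1.3 / 1.5 = 0.87 |
| 0.40 | 0.50 | 2 | 1.4 / 1.5 = 0.93 |

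With the two prevalences exchanged, the factor becomes the inverse, from 1 / 0.76 = 1.32 down to 1.5 / 1.4 = 1.07. These are factors on a crude ratio. The planned model also adjusts for past anemia, a plausible consequence of heavy bleeding, so the residual factor is probably closer to 1.

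**The case against.** Four points can be made in defence of the plan.

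- **The open line in question 18 can capture a bleeding disorder.** It asks about serious diseases diagnosed by a physician, and SAP 6.1 codes diagnoses to ICD-10. This stands in part: collection is possible, though unprompted, and a blank does not mean absent. A reader might infer that the covariate will be almost empty, but that is a statement about data the documents do not show. The supportable statement is that there is no dedicated item and no named source.
- **The wording in Table D-1.1.2 may already mean question 11.** A history of bleeding fits that item at least as well as a coagulation disorder. If so, nothing is omitted and only the label needs correcting. No section links the two and none rules the link out, so it cannot be asserted that baseline heavy bleeding is left out of the model.
- **The covariate list is not final, and other adjustment exists.** The council has the last word, Appendix III adds user type at follow-up, and protocol section 11 promises alternative analyses with other baseline risks. All true, but the council needs an identifiable variable to decide on, and SAP 5.4.2 specifies no such alternative analysis.
- **Question 11 is imperfect.** It is a tick-all-that-apply list of current symptoms with no box for none, so an unticked box may mean no or unanswered. In switchers it may reflect bleeding under the previous hormonal treatment. These are real limits and need a coding rule, but they are no reason to leave the item unnamed.

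**Conclusion.** The traceability gap is established. One of the three anemia covariates in SAP 5.4.2 has no dedicated baseline item and no derivation rule, and its label differs between the protocol, the SAP text and the table that reports the result. A collected item with a plausible link to the outcome is named in no covariate list.

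The consequence is conditional: the adjusted anemia hazard ratio may carry residual confounding by baseline bleeding. A reader might infer that it is confounded by indication, or that a true hazard ratio of 2.0 would appear as 2.0 × 0.76 = 1.52. The documents support neither. The 0.76 is the most extreme of four assumed scenarios, applies to a crude ratio, and ignores the adjustment for past anemia. The direction of any imbalance is unknown. The range of 0.76 to 0.93, or its inverse, shows only that the choice of variable could matter for a comparison against 2.

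**What to change.** 1. Name question 11, heavy or irregular bleeding at baseline, as a covariate of the anemia model in SAP 5.4.2, Appendix III and the footnote of Table D-1.1.2.
2. Put its coding in Appendix IV: ticked or not ticked, and missing if the whole of question 11 is blank.
3. Keep history of bleeding disorders only if its source is defined, for example as specified ICD-10 codes from the open line of question 18.
4. Use one label for each term in all three places, and state why the family history named in protocol section 11 is not used.
5. Submit the revised list to the council for its decision.

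The cost is SAP wording and one more model term; the item is already collected. The limitation in switchers should be stated next to the definition.

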Crude as well as adjusted hazard ratios will be calculated. The appropriate confounding variables will be built into the statistical model. Based on the expectation of a small absolute number of serious outcomes of interest the number of confounding variables will be limited to established risk factors for these outcomes. For anemia these will include age, duration of current use, and family history of bleeding disorders and a past history of anemia. For depression, age, chronic pelvic pain, anxiety disorder and a family history of depression are proposed. For 'treatment failure' chronic pelvic pain, age and previous surgical treatment will be included. The final decision on and the addition of other confounding variables (e.g. country) will be made by the Safety Monitoring and Advisory Council before the first interim analysis of follow-up data. In addition, alternative analysis will be performed with other potential baseline risks to check the appropriateness of this decision.

A detailed statistical analysis plan will be developed by the Principal Investigator during the first year after study start. The final analysis plan will be approved by the Safety Monitoring and Advisory Council before the first interim analysis of follow-up data.

Biannual interim reports will be provided to the funder following release of the interim analyses results by the independent Safety Monitoring and Advisory Council (cf. section 13).

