Medical History  18. Have you ever been told	by a physic	an that you had or have any of the following diseases or conditions? Please
		condition was treated by a physician.
Deep venous thrombosis 57 (blood clot in the deep veins e.g. legs/arms)	□ No	☐ Yes, in MMM Self Y Y Y Y Y Self Self Self Self Self Self Self Self
logarams/		I was treated by a physician 60 □ Yes □ No
		I was treated with blood-thinning drugs ₅₁ ☐ Yes ☐ No
Pulmonary embolism 62 (blood clot in the lung)	□ No	Yes, in  M, M, Y, Y, Y, Y,  month 63 year 64
		I was treated by a physician ⊕5 ☐ Yes ☐ No
		I was treated with blood-thinning drugs ₅ □ Yes □ No
Myocardial infarction 67 (heart attack)	□ No	Yes, in
		I was treated by a physician 70 ☐ Yes ☐ No
		If yes, was an ECG performed? ₁₁ ☐ Yes ☐ No
		Was the infarction confirmed by an ECG? ₁₂ ☐ Yes ☐ No
Stroke 73	□ No	Yes, in  M M 74 Y Y Y Y 75
		I was treated by a physician 76 ☐ Yes ☐ No
Anemia 77	□ No	Yes, diagnosed in worth 78 year 79
		I was treated by a physician 80 □ Yes □ No
		I received a blood or iron trans-/infusion 81 ☐ Yes ☐ No
		I took iron tablets 82 ☐ Yes ☐ No
Depression requiring treatment 83	□ No	☐ Yes, diagnosed in [M N set Y Y Y Y Y Y Set Y year Y Set Y year Y Set Y Y Y Y Y Y Set Y Y Y Y Y Y Y Y Y Y Y Y Y Y Y Y Y Y Y
		I was treated by a general practitioner 86 ☐ Yes ☐ No
		I was treated by a psychiatrist 87 ☐ Yes ☐ No
		I was admitted to hospital 88 ☐ Yes ☐ No
		There was a suicide attempt № □ Yes □ No
Cancer 90 (e.g. Breast cancer)	□No	☐ Yes, diagnosed in [M, M] [Y, Y, Y, Y] [92] year
		What kind of cancer?
		I was treated by a physician 94 ☐ Yes ☐ No
Other serious diseases 95 (e.g. hypertension, diabetes, benign	□ No	☐ Yes, which?
tumor)		1
		I was treated by a physician ₅ □ Yes □ No
		2 When? M.M. Y.Y.Y.Y.Y.
		I was treated by a physician ☐ Yes ☐ No
		If you have had more than 2 serious diseases, please use the space in the comment section on page 4.
Operations 100	□ No	☐ Yes, I had operation(s), which?
(excluding those listed in Q14)		1
		2 When?
		If you have had more than 2 operations, please use the space in the comment section on page 4.

3

Supporting document SOP BMT 01.09 – Doc 5002.02 – Effective date 21.03.2017

Relat	tives				
19.	-	or sister(s) been diagnosed	d with endometriosis?		
	□ None 104	☐ Mother 105	☐ Sister	. ,	
20.		parent(s) or sibling(s) beer			1 P
	□ None 107	☐ Mother 108	☐ Fathe		bling(s) 110
21.	(blood clot in the I	•	•	, ,	

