## IV List of derived variables

Variable Label	Definition
BMI	Weight (kg) / ( Height(cm) / 100 ) 
BMI categories	< 20, 20 to <25, 25 to < 30, 30 to < 35, >=35
Age categories	< 20 years, 20 to < 30 years, 30 to < 40 years, >= 40 years
Feeling like a failure	Never = 4, Rarely = 3, Sometimes = 2, Often = 1, Always = 0
Felling down, depressed or hopeless	Never = 4, Rarely = 3, Sometimes = 2, Often = 1, Always = 0
Feeling happy or optimistic about the future	Never = 0, Rarely = 1, Sometimes = 2, Often = 3, Always = 4
Mood Score	The response to the three mood-related questions ("Feeling like a failure", "Felling down, depressed or hopeless" and "Feeling happy or optimistic about the future") is scored from 0 to 4, with 4 representing the most positive mental state. The scores of the responses to the three mood questions are then summarized into a single comprehensive Mood Score and transformed to a 0 to 100-point scale. A higher score indicates a better mood. Missing scores for a single mood question are replaced by last observation carried forward (LOCF).
Time since first endometriosis symptoms	< 6 months, 6 months to < 1 year, 1 to < 2 years, 2 to < 5 years, 5 to < 10 years, >= 10 years
Time since first diagnosis of endometriosis	< 6 months, 6 months to < 1 year, 1 to < 2 years, 2 to < 5 years, 5 to < 10 years, >= 10 years
Time span between first endometriosis symptoms and diagnosis	< 6 months, 6 months to < 1 year, 1 to < 2 years, 2 to < 5 years, 5 to < 10 years, >= 10 years
Pain severity score	0 to 3 (mild), 4 to 7 (moderate), 8 to 10 (severe)

Supporting document SOP BMT 01.09 – Doc 5002.02 – Effective date 21.03.2017

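### The depression model omits the study-entry Mood Score and drops anxiety disorder without explanation, so baseline mental state is incompletely controlled

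*SAP*

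**What the plan says.** Protocol section 11 states: "For depression, age, chronic pelvic pain, anxiety disorder and a family history of depression are proposed". Section 6 also plans a baseline questionnaire covering "detailed history of previous treatments for endometriosis, anemia and psychiatric illnesses".

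The SAP gives two lists for depression, and neither contains anxiety disorder or mood:

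- Section 5.4.2: "Age, family and personal history of depression, use of Antidepressants/SSRI".
- Appendix III: "EMT user type at follow-up, age, family and personal history of depression, use of Antidepressants/SSRI, severity of pain".

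Section 5.4.2 makes history and pain severity time-invariant, but states: "EMT user type at follow up, use of Antidepressants/SSRI and current or worsening depression (primary outcome) will be included as time-dependent cofactors".

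In the baseline questionnaire (SAP Appendix I), the one psychiatric entry in question 18 is "Depression requiring treatment 83" (the number is a field code). It asks for the date of diagnosis, treatment by a general practitioner or psychiatrist, hospital admission and suicide attempt. Question 18 also has an open entry, "Other serious diseases 95", whose printed examples are all somatic. Question 16 records regular medication. Questions 22a to 22c ask about mood. For these, Appendix IV says: "The scores of the responses to the three mood questions are then summarized into a single comprehensive Mood Score", rescaled to 0 to 100. The score is tabulated in Section B-8 only.

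**The concern.** Treatment is chosen by the physician, so the depression comparison depends on covariate adjustment. The outcome includes worsening of existing depression (SAP 5.4.3), which makes mental state at treatment start an obvious candidate confounder. The Protocol's introduction records a continuing worry that progestogens aggravate depressive symptoms. If prescribers act on that worry, women with low mood would be channelled away from dienogest (DNG) and the hazard ratio would be biased downwards, towards non-inferiority. If women in worse condition are moved to the new drug, the bias runs upwards and costs power.

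The covariates in the model cover this only in part. Treated depression in the past does not capture untreated low mood and does not grade current severity. Antidepressant use after baseline can be a consequence of the depression being counted, or of the treatment, so a time-dependent term is not a clean adjustment for the starting state.

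**Working it through.** **The plan's own figure.** SAP Table 3 uses one-sided alpha 0.0083, 90% power, margin 2, a rate of 0.01 per woman-year and 2:1 exposure. Schoenfeld's formula gives

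events = (2.395 + 1.282)² / [(2/3)(1/3)(ln 2)²] = 13.52 / 0.1068 = 126.6.

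At 0.01 per woman-year this is 12,663 women-years: 8,442 DNG and 4,221 reference. Dividing 8,442 by 10% gives about 84,400 in total. The plan states 8,400, 4,200 and 84,000, so its figures reproduce. They imply 84 + 42 = 126 events. None of them depends on the covariates.

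**Bias from an unadjusted binary factor.** The documents give no prevalence of low mood by cohort and no effect size, so every input here is an assumption. With prevalence p1 in DNG users, p0 in the reference cohort (OAED) and rate ratio k, the hazard ratio is multiplied by

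B = [1 + p1(k − 1)] / [1 + p0(k − 1)].

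| p1 | p0 | k | B |
|---|---|---|---|
| 0.25 | 0.30 | 2 | 1.25/1.30 = 0.96 |
| 0.25 | 0.35 | 3 | 1.50/1.70 = 0.88 |
| 0.20 | 0.40 | 4 | 1.60/2.20 = 0.73 |
| 0.25 | 0.20 | 1.5 | 1.125/1.10 = 1.02 |
| 0.40 | 0.20 | 2 | 1.40/1.20 = 1.17 |
| 0.40 | 0.20 | 4 | 2.20/1.60 = 1.38 |

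**Effect on the test.** With 126 events at 2:1, 1/SE of the log hazard ratio is √(126 × 2/9) = 5.292. At a true hazard ratio of 2, the chance of declaring non-inferiority is Φ(5.292 × ln(1/B) − 2.395):

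- B = 1: 0.0083
- B = 0.96: 0.014
- B = 0.88: Φ(0.66 − 2.395) = 0.04
- B = 0.73: 0.24

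These hold the count at 126. At a true hazard ratio of 2 over the same women-years there would be 168 + 42 = 210 events, SE = √(1/168 + 1/42) = 0.1725, and the figure for B = 0.88 becomes Φ(0.125/0.1725 − 2.395), about 0.05.

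In the other direction, at a true hazard ratio of 1 and B = 1.17, power is Φ(5.292 × ln(2/1.17) − 2.395) = Φ(0.44) = 0.67, against 0.90 planned.

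**Room for extra terms.** Exposure, age, two history terms and antidepressant use make 5 terms: 126/5 = 25.2 events per term. Adding the Mood Score gives 126/6 = 21.0; adding anxiolytic use as well gives 126/7 = 18.0. At the SAP's minimum of 5 events per group the figures would be 10/5 = 2.0 and 10/6 = 1.7, too few for either model.

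**The case against.** The case for the plan has several sound parts.

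- The SAP adjusts for personal history of depression, which the Protocol's list lacked, and for family history and antidepressant use. The bias factors above assume no adjustment, so they overstate what would remain.
- The history item records timing and severity of past care, and current medication is recorded. Anxiety could also surface in the free text or in the psychotropic drug table (B-6.4).
- The Protocol limits covariates to established risk factors because few events are expected, leaves the final choice to the Safety Monitoring and Advisory Council, and promises alternative analyses with other baseline risks.
- The Mood Score is a three-item sum with no validation cited. Switchers' entry mood may reflect earlier hormonal treatment, and women may take the prescription home before deciding to join, so the score need not precede first intake.

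The first two points rule out a stronger reading, that baseline mental state is uncontrolled or unmeasured. A reader might also infer that a biased estimate just below 2 would pass. It would not: the rule uses the upper confidence limit, and with 126 events the observed hazard ratio must be below 2/exp(2.395/5.292), about 1.27. Nor do the documents show that low-mood women are steered away from DNG, so the direction is open.

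The third point does not settle the matter. The SAP specifies no alternative analysis for depression, so nothing ensures that baseline mood is examined. The fourth argues for care in interpretation and makes a sensitivity model acceptable; it does not justify leaving the score out of every model.

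**Conclusion.** The concern holds in a limited form. A confounder proposed in the Protocol has no dedicated baseline item and disappears from the SAP without a reason. The one direct rating of current mood is collected and then left out of the depression model. Control of baseline mental state is incomplete, and the residual bias could favour or disfavour DNG.

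The size cannot be read from the documents. Under the assumed inputs and no adjustment, factors of 0.73 to 0.96 arise if low mood is rarer among DNG users, and 1.02 to 1.38 if it is commoner. For the middle scenario (0.88), the one-sided error at a true hazard ratio of 2 is about 0.04 with 126 events. This is an upper bound for that scenario and event count, because the existing covariates remove part of the bias. The planned sample size is unaffected.

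**What to change.** - Add the study-entry Mood Score, continuous and at its study-entry value only, to the depression row of SAP 5.4.2 and to Appendix III. Later scores should not enter, since they may lie on the path from treatment to outcome. If confirmed events are few, make this a named, prespecified sensitivity model that fulfils the alternative analyses promised in Protocol section 11.
- In that analysis, fix antidepressant use at its study-entry value, and add baseline anxiolytic use from the ATC coding behind Table B-6.4 as a partial proxy for anxiety disorder.
- State why anxiety disorder was dropped. While editing, reconcile the two depression lists, which differ on pain severity and user type.

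The cost is SAP wording and one or two terms from data already held: about 25 events per term falls to 21 with the Mood Score, or 18 with both. Missing mood items need a rule. Appendix IV carries the last observation forward, but at study entry there is no earlier value, so the SAP must provide a missing category or accept that those women leave the adjusted model.
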